4.2 Selection of Study Population

4.2.1 Inclusion Criteria

Patients may be enrolled in the study only if they meet all of the following criteria:

- 1. Patients have voluntarily agreed to participate by giving written informed consent
- 2. Age 18 years (including 18 years) on the day of signing informed consent
- 3. Patients meet the following eligibility criteria for the corresponding part of the study:
 - 1) Phase 1 Portion:
 - a) The patients must have a histologically or cytologically confirmed locally advanced or metastatic TNBC, or high-grade, non-mucinous, epithelial ovarian cancer (including fallopian or primary peritoneal cancer) for which no effective standard therapy is available
 - b) *BRCA1* and *BRCA2* mutations are not required but enrichment of this patient population is preferred
 - c) Patients must agree to retrospective germline BRCA testing using blood samples
 - d) Archival tumor tissues will be collected, if available
 - 2) Phase 2 Portion:
 - a) Patients who have histologically or cytologically confirmed high-grade (Grade 2 or Grade 3 endometrioid epithelial cancer is acceptable too), non-mucinous, epithelial ovarian cancer (including fallopian, or primary peritoneal cancer), harboring germline *BRCA1/2* mutation and must meet the following criteria:
 - i. Patients must have received at least 2 lines of standard chemotherapy, currently with relapsed/progressive disease or have withdrawn due to unacceptable toxicity from most recent standard treatment
 - ii. Platinum-sensitive or platinum-resistant patients (Patients are defined as platinum sensitive if disease progression by RECIST, version 1.1, had occurred ≥ 6 months after their last platinum treatment, while platinum-resistant is defined if disease progression occurred < 6 months after the

last platinum treatment

- iii. If mixed histology, >50% of the primary tumor had to be confirmed to be high-grade (Grade 2 or Grade 3 endometrioid epithelial cancer is acceptable too), non-mucinous, epithelial ovarian cancer
- b) All patients will be required to undergo germline *BRCA1/2* mutation testing using blood samples prior to enrolment
- c) Archival tumor tissues will be collected, from all patients, if available
- 4. Patients must have measurable disease as defined per the RECIST, version 1.1
- 5. Eastern Cooperative Oncology Group (ECOG) performance status of ≤ 1 (Appendix 3)
- 6. Life expectancy ≥ 12 weeks

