APPENDIX 5: THE RESPONSE EVALUATION CRITERIA IN SOLID TUMORS (RECIST) GUIDELINES

The text below was obtained from the following reference: Eisenhauer EA, Therasse P, Bogaerts J, Schwartz LH, Sargent D, Ford R, et al. New response evaluation criteria in solid tumors: revised RECIST guideline (Version 1.1). *Eur J Cancer* 2009;45:228-247.

DEFINITIONS

Response and progression will be evaluated in this trial using the international criteria proposed by the Response Evaluation Criteria in Solid Tumors (RECIST) Committee (Version 1.1). Changes in only the largest diameter (uni-dimensional measurement) of the tumor lesions are used in the RECIST criteria. Note: Lesions are either measurable or non-measurable using the criteria provided below. The term "evaluable" in reference to measurability will not be used because it does not provide additional meaning or accuracy.

Measurable Disease

Tumor lesions: Must be accurately measured in at least 1 dimension (longest diameter in the plane of measurement is to be recorded) with a minimum size of:

- 10 mm by CT scan (irrespective of scanner type) and MRI (no less than double the slice thickness and a minimum of 10 mm).
- 10 mm caliper measurement by clinical exam (when superficial).
- 20 mm by chest X-ray (if clearly defined and surrounded by aerated lung).

Malignant lymph nodes: To be considered pathologically enlarged and measurable, a lymph node must be ≥ 15 mm in short axis when assessed by CT scan (CT scan slice thickness recommended to be no greater than 5 mm). At baseline and in follow-up, only the short axis will be measured and followed.

Non-measurable Disease

All other lesions (or sites of disease), including small lesions (longest diameter ≥ 10 to <15 mm with conventional techniques or < 10 mm using spiral CT scan), are considered non-measurable disease. Leptomeningeal disease, ascites, pleural, or pericardial effusion, inflammatory breast disease, lymphangitic involvement of skin or lung, abdominal masses/abdominal organomegaly identified by physical examination that is not measurable by reproducible imaging techniques are all non-measurable.

21 September 2018

Bone lesions:

- Bone scan, PET scan, or plain films are not considered adequate imaging techniques to measure bone lesions. However, these techniques can be used to confirm the presence or disappearance of bone lesions

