coronal). The smaller of these measures is the short axis. For example, an abdominal node which is reported as being 20 mm x 30 mm has a short axis of 20 mm and qualifies as a malignant, measurable node. In this example, 20 mm should be recorded as the node measurement. All other pathological nodes (those with short axis \geq 10 mm but <15 mm) should be considered non-target lesions. Nodes that have a short axis <10 mm are considered non-pathological and should not be recorded or followed.

A sum of the diameters (longest for non-nodal lesions, short axis for nodal lesions) for all target lesions will be calculated and reported as the baseline sum diameters. If lymph nodes are to be included in the sum, then as noted above, only the short axis is added into the sum. The baseline sum diameters will be used as reference to further characterize any objective tumor regression in the measurable dimension of the disease.

Non-target Lesions

All other lesions (or sites of disease) including pathological lymph nodes should be identified as non-target lesions and should also be recorded at baseline. Measurements are not required and these lesions should be followed as "present", "absent", or in rare cases "unequivocal progression" (more details to follow). In addition, it is possible to record multiple non-target lesions involving the same organ as a single item on the case record form (eg, "multiple enlarged pelvic lymph nodes" or "multiple liver metastases").

GUIDELINES FOR EVALUATION OF MEASURABLE DISEASE

All measurements should be recorded in metric notation, using calipers if clinically assessed. All baseline evaluations should be performed as close as possible to the treatment start and never more than 4 weeks before the beginning of the treatment.

The same method of assessment and the same technique should be used to characterize each identified and reported lesion at baseline and during follow-up. Imaging based evaluation should always be done rather than clinical examination unless the lesion(s) being followed cannot be imaged but are assessable by clinical examination.

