#### **6 STATISTICAL METHODS**

#### 6.1 ANALYSIS SETS

The Safety Analysis Set includes all patients who received at least one dose of pamiparib.

The Efficacy Evaluable Analysis Set includes all patients in the safety analysis set who had measurable disease at baseline per RECIST, v1.1 (based on investigator assessment for phase 1 and IRC assessment for phase 2) and had at least one post baseline tumor assessment unless discontinued treatment due to clinical progression or death prior to tumor assessment.

The DLT Analysis Set includes all patients who received at least 75% of pamiparib or who experienced a DLT event during the DLT observation period (Cycle 1).

The PK Analysis Set includes all patients for whom valid pamiparib PK parameters can be estimated.

Version 1.1: 02/28/2020 Page 10 of 28

The CA-125 Evaluable Analysis Set is defined as the subset of patients in the Safety Analysis Set with baseline CA-125  $\geq$  2 x ULN. This will be the primary analysis set for the analysis of CA-125 response rate.

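### Appendix 5 contradicts itself on non-nodal lesions of 10 to <15 mm read on non-spiral CT, and possibly on MRI or by caliper

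*Protocol*

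**What the plan says.** Protocol Appendix 5, under Measurable Disease, sets the minimum longest diameter for a tumor lesion by technique:

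- CT and MRI: "10 mm by CT scan (irrespective of scanner type) and MRI (no less than double the slice thickness and a minimum of 10 mm"
- Clinical examination: "10 mm caliper measurement by clinical exam (when superficial"
- Chest X-ray: "20 mm by chest X-ray (if clearly defined and surrounded by aerated lung"

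The Non-measurable Disease paragraph that follows begins "All other lesions (or sites of disease), including small lesions (longest diameter ≥ 10 to <15 mm with conventional techniques" and continues "with conventional techniques or < 10 mm using spiral CT scan), are considered non-measurable disease". The opening note of the appendix treats the two classes as mutually exclusive.

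Lymph nodes have a separate rule based on the short axis. They are measurable from 15 mm, and the Target Lesions text sends smaller ones to the non-target list ("All other pathological nodes (those with short axis" from 10 to below 15 mm).

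Three parts of the plan depend on this classification:

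- Inclusion criterion 4 in protocol section 4.2.1: "Patients must have measurable disease as defined per the RECIST, version 1.1".
- Target-lesion selection in Appendix 5, which draws on measurable lesions only.
- The efficacy evaluable set, which SAP section 6.1 limits to patients with "measurable disease at baseline per RECIST, v1.1 (based on investigator assessment for phase 1 and IRC assessment for phase 2".

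Protocol sections 7.5.1 and 7.5.2 point to Appendix 5 as the RECIST text for investigator assessment.

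**The concern.** A 12 mm peritoneal implant read on non-spiral CT is measurable under one paragraph and non-measurable under the next. A site that follows the second paragraph could turn away a patient whose only disease is of that kind, or could record the lesion as non-target in a patient who enters on other disease. A reader who follows the first paragraph would measure it. The two reads would then start from different baseline sums and could reach different response calls on the same scans.

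Protocol section 10.3.1 and SAP section 6.4.1 present the investigator-assessed results as a sensitivity analysis for the independent review. Part of any disagreement between the two could therefore come from the definition rather than from the reading. Phase 2 is planned for 25 to 35 centers, and each must work out for itself what the undefined term covers.

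**Working it through.** **1. The plan's own figure.** Inputs from protocol section 10.1 and SAP section 5: n = 80 evaluable platinum-sensitive patients, null ORR 30%, assumed ORR 52%, exact binomial test at 0.025. The test is one-sided (protocol section 10.3.1).

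- Smallest r with P(X ≥ r | 80, 0.30) ≤ 0.025: r = 33 (41.25%), attained alpha 0.0211.
- Power = P(X ≥ 33 | 80, 0.52) = 0.979. The stated 98% reproduces.

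**2. Both paragraphs applied to one lesion.** Take a non-nodal lesion of 12 mm longest diameter. CT slices are 5 mm, as section 7.3.4 requires. MRI slices are at most 6 mm, so that twice the thickness does not exceed 12 mm.

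| Technique | Measurable paragraph | Non-measurable paragraph | Result |
|---|---|---|---|
| Spiral CT | measurable (12 ≥ 10) | not listed (12 is not <10) | agree |
| Non-spiral CT | measurable (12 ≥ 10) | listed (10 to <15) | conflict |
| MRI | measurable (12 ≥ 10) | listed only if a conventional technique | conditional conflict |
| Caliper, superficial lesion | measurable (12 ≥ 10) | listed only if a conventional technique | conditional conflict |
| Chest X-ray | not measurable (12 < 20) | non-measurable | agree |

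The result is the same at 10 mm and at 14.9 mm. Below 10 mm, and from 15 mm upward, no technique gives a conflict. Non-spiral CT is an outright conflict because the second paragraph sets conventional techniques against spiral CT, while the first says that scanner type does not matter.

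**3. Whether the affected techniques can occur.** Table 7, footnote 13, allows CT or MRI. Section 7.3.4 directs patients at increased risk of contrast allergy to MRI. It fixes CT slices at 5 mm but does not say whether acquisition must be spiral. The routes are therefore open, but the documents do not show how often they are used.

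**4. How a response call could change.** This is a constructed example, not trial data. Two lesions of 30 and 12 mm shrink to 22 and 5 mm. Appendix 5 sets PR at a decrease of at least 30% in the sum of target lesions.

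- Both lesions are targets: 30 + 12 = 42 mm, 22 + 5 = 27 mm, and (27 − 42)/42 = −35.7%, which is PR.
- Only the larger is a target: (22 − 30)/30 = −26.7%, which is SD, with the smaller lesion a persisting non-target lesion.
- One changed call in 80 patients: 1/80 = 1.25 percentage points of ORR.

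**5. Power if patients left the evaluable set.** The number whose sole measurable disease lies in the band is not given, so a range is assumed. Power is at ORR 52%.

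| Leave the set | n | Critical value | Power |
|---|---|---|---|
| 0 | 80 | 33 | 97.9% |
| 4 | 76 | 32 | 96.7% |
| 8 | 72 | 30 | 97.0% |
| 12 | 68 | 29 | 95.2% |
| 16 | 64 | 28 | 92.6% |
| 20 | 60 | 26 | 93.0% |

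The column is not monotone because the critical value is a whole number.

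**The case against.** The best defense is that non-measurable disease is a residual class. The sentence opens by referring to all other lesions, so a 12 mm lesion that already qualified above never reaches it, and the parenthesis only illustrates. That is a fair account of the intent, but it does not remove the conflict. The parenthesis names the 10 to <15 mm band as belonging to the residual class. On a purely residual reading, that band would be empty for CT at the required slice thickness and for caliper.

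A second defense is that conventional techniques means plain radiography. The appendix does not say so, and a band ending at 15 mm does not match its 20 mm X-ray cut-off. Nor is the clause the nodal rule, because it uses longest diameter and nodes use the short axis. A reader might infer that the nodal band was misplaced here. The documents show that a nodal band with the same limits exists, but nothing about how the text came to be drafted.

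A third defense is that criterion 4 and the analysis sets cite RECIST version 1.1, not the appendix. Sections 7.5.1 and 7.5.2 nevertheless make Appendix 5 the working text for investigators.

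Several limits stand in full. The documents do not establish that MRI or caliper counts as a conventional technique. They do not show that any site uses non-spiral CT. They include no charter for the independent review, so it cannot be said that sites and independent readers would follow different paragraphs. SAP section 6.1 gives the Phase 2 judgment of baseline measurability to the independent review, and SAP section 6.4.1 bases the hypothesis test on its data.

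**Conclusion.** The contradiction is real and narrow. It covers non-nodal lesions of 10 to <15 mm longest diameter: outright on non-spiral CT, and on MRI or by caliper only if those are conventional techniques. Nothing else in the documents resolves it. It can affect:

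- site screening, where such a lesion is the patient's sole measurable disease;
- the investigator's target-lesion choice, for any such lesion;
- through these, the investigator-assessed ORR.

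Three stronger readings are tempting, and the documents do not support them. The first is that every non-nodal lesion in the band is classed both ways; spiral CT and chest X-ray give a single answer. The second is that the primary test rests on contradictory definitions. It uses independently judged measurability and response, so it is touched only through who is enrolled, or if the independent readers also apply the second paragraph. The third is that power is at risk. The 98% reproduces, and power stays above 92% in every assumed scenario up to 20 of 80 patients leaving the set.

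The number of patients affected is unknown, so no total effect on ORR can be given beyond 1.25 points per changed call in 80. I class this as an inconsistency of low severity.

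**What to change.** In Appendix 5, Non-measurable Disease, replace the parenthesis with: longest diameter <10 mm, or pathological lymph nodes with short axis ≥10 to <15 mm. Delete the references to conventional techniques and to spiral CT. Keep the existing slice-thickness rules and the 20 mm chest X-ray rule; lesions that fail those remain non-measurable through the residual wording. Every cut-off is already in the appendix.

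Confirm to sites and to the independent readers that the same cut-off applies to both. If enrolment is complete, document before database lock which cut-off each side used, and list any lesions of 10 to <15 mm that were classed differently.

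The cost is one sentence in an appendix and a memo, with no added assessments. If enrolment is complete, add a short listing.

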APPENDIX 6: CHRONIC KIDNEY DISEASE EPIDEMIOLOGY COLLABORATION (CKD-EPI) EQUATION

In adults, the most widely-used equations for estimating glomerular filtration rate (eGFR) from serum creatinine are the Chronic Kidney Disease Epidemiology Collaboration (CKD-EPI) Equation and the Modification of Diet in Renal Disease (MDRD) Study equation. The National Kidney Disease Education Program (NKDEP) calculators rely on creatinine determinations which are isotope dilution mass spectrometry (IDMS) traceable. All laboratories should be using creatinine methods calibrated to be IDMS traceable. Read more about creatinine standardization.

This CKD-EPI equation calculator should be used when Scr reported in mg/dL. This equation is recommended when eGFR values above $60 \text{ mL/min}/1.73 \text{ m}^2$ are desired.

GFR = $141 \times \min(\text{Scr}/\kappa, 1)\alpha \times \max(\text{Scr}/\kappa, 1)-1.209 \times 0.993\text{Age} \times 1.018$ [if female] $\times 1.159$ [if black]

where:

Scr is serum creatinine in mg/dL,

 κ is 0.7 for females and 0.9 for males,

 α is -0.329 for females and -0.411 for males,

min indicates the minimum of Scr / κ or 1, and

max indicates the maximum of Scr / κ or 1.

The equation does not require weight because the results are reported normalized to 1.73 m² body surface area, which is an accepted average adult surface area.

The online calculator for CKD-EPI can be found here: https://www.niddk.nih.gov/health-information/health-communication-programs/nkdep/lab-evaluation/gfr-calculators/Pages/gfr-calculators.aspx

APPENDIX 7: EVALUATION OF RESPONSE ACCORDING TO CA-125

The text below was obtained from the following reference: Gordon John Sampson Rustin, etc. Definitions for Response and Progression in Ovarian Cancer Clinical Trials Incorporating RECIST 1.1 and CA-125 Agreed by the Gynecological Cancer Intergroup (GCIG). *Int J Gynecol Cancer*. 2011;21: 419-423.

Definition of Response:

A CA-125 response is defined as at least a 50% reduction in CA-125 levels from a pretreatment sample. The response must be confirmed and maintained by using the next scheduled CA-125 data (at least 28 days). Patients can be evaluated according to CA-125 only if they have a pretreatment sample that is at least twice the upper limit of the reference range and within 2 weeks before starting the treatment.

To calculate CA-125 responses accurately, the following rules apply:

- Intervening samples and the 28-day confirmatory sample must be less than or equal to (within an assay variability of 10%) the previous sample.
- Variations within the reference range of CA-125 levels will not interfere with the response definition.
- For each patient, the same assay method must be used, and the assay must be tested in a quality control scheme.
- Patients are not evaluable by CA-125 if they have received mouse antibodies (unless the assay used has been shown not to be influenced by human antimouse antibody4, 5) or if there has been medical and/or surgical interference with their peritoneum or pleura during the previous 28 days (eg, paracentesis). If assessing therapy that includes 2 treatment modalities for relapse (eg, surgery and chemotherapy), any CA-125 response results from both treatment modalities. CA-125 cannot distinguish between the effects of the 2 treatments.

The date when the CA-125 level is first reduced by 50% is the date of the CA-125 response. To calculate response, an intent-to-treat analysis should be used that includes all patients with an initial CA-125 level of at least twice the upper limit of the reference range as eligible and evaluable. In addition, as a separate analysis, those patients who have a CA-125 response and whose CA-125 level falls to within the reference range can be classified as CA-125 complete responder see Table 5 for Phase 1, and Table 7 for Phase 2 where CA-125 is stated as normalized or normal, means within the reference range. Patients who have a fall of CA-125 to within the reference range but whose initial CA-125 was less than twice the upper limit of the reference range cannot therefore be classified as a CA-125 complete responder.

Table 11. CA-125 response measurement

CA-125 level	CA-125 measurement
Baseline CA-125 more than twice upper limit of normal, later reduced by	Complete response (CR)
50% to normal and maintaining for at least 28 days	
Baseline CA-125 more than twice upper limit of normal, later reduced by	Partial response (PR)
50% but not to normal	
CA-125 change out of range of PR and PD	Non-PR, non-PD
CA-125 increased at baseline returning to normal after treatment, later	Progressive disease (date of first
twice or higher upper limit of normal (two consecutive measurement at	evaluation of progression)
interval of at least one week)	
CA-125 increased at baseline not returning to normal after treatment,	Progressive disease (date of first
later twice or higher the lowest value (two consecutive measurement at	evaluation of progression)
interval of at least one week)	
CA-125 within reference range at baseline, later twice or higher upper	Progressive disease (date of first
limit of normal (two consecutive measurement at interval of at least one	evaluation of progression)
week)	

Reporting of response according to GCIG criteria that integrate CA-125 response with RECIST1.1 is shown in Table 12 and Table 13.

CA-125	Nontarget Lesions*	New Lesions	Overall Serological Response	Best Response for This Category Also Requires
Response and Normalized	CR	No	CR	Confirmed and maintained for at least 28 days
Response	Non-PD	No	PR	
Normalized but no response	Non-CR/Non- PD	No	SD	
Non-PR/non-PD	Non-PD	No	SD	
PD	Any	Yes or No	PD	
Any	PD†	Yes or No	PD	
Any	Any	Yes	PD	

Table 12.	Evaluation of best overall response in patients without initial measurable disease
and who are	evaluable by CA-125

CR, Complete response; PD, progressive disease; PR, partial response; SD, stable disease.

*Nontarget lesions include ascites and peritoneal thickening, which are not measurable according to RECIST, version 1.1.

†Unequivocal progression in nontarget lesions may be accepted as disease progression.

Target	Nontarget	New	CA-125	Overall	Best Response for This
Lesion*	Lesions†	Lesions		Best	Category Also
				Response	Requires
CR	CR	No	Normal	CR	Best RECIST 1.1
CR	Non-CR	No	Not PD	PR	response for CR and PR
	Non-PD				also required it to be
CR	CR	No	PR but not	PR	confirmed and maintained
			normal		for at least 28 days if
CR	NE	No	PR	PR	response is primary
PR	Non-PD or	No	Not PD	PR	endpoint
	NAE				
NAE	Non-PD	No	PR	PR	
PD or New >28 days from CA-125 PR‡		PR	PR		
SD§	Non-PD	No	PR	PR	
SD§	Non-PD or	No	Not PR and	SD	
	NAE		not PD		
PD or New<28 days from CA-125 PR‡		PR	PD		
PD	Any	Yes or No	Any	PD	
Any	PD	Yes or No	Any	PD	
Any	Any	Yes	Any	PD	
Any	Any	Yes or No	PD	PD	

Table 13.	Best overall response in patients with measurable disease and who are also
evaluable by	CA-125

NE, Not evaluated; NAE, not all evaluated.

*Target lesions include up to 5 measurable lesions (2 per organ) as defined by RECIST 1.1.

[†]Nontarget lesions include ascites and peritoneal thickening which are not measurable according to RECIST 1.1. [‡]Patients who have a CA-125 response that occurs more than 28 days from PD according to RECIST 1.1 are considered a PR, according to best response, but PD if the RECIST 1.1 PD is within 28 days (including) of CA-125 response. §The protocol should specify the minimum time interval between 2 measurements for classification as stable disease.

